Timing of initiation of anticoagulants for prophylaxis of thrombosis following total knee replacement is a balance between safety and efficacy. Dosing closer to the time of surgery may confer additional efficacy but at the expense of increased bleeding risk. Apixaban and enoxaparin will be started at 12 to 24 hours post-operatively, consistent with labeled dosing regimens and REGN9933 will also be dosed at 12 to 24 hours post-surgery, to allow a direct comparison. Dosing of FXI inhibitors in this time range, as well as pre-operatively, has been shown to be well-tolerated in published trials of FXI inhibitors ([Büller, 2015](#)) ([Verhamme, 2021](#)) ([Weitz, 2020](#)).

Regarding duration of treatment, for subjects assigned to study drug treatment with enoxaparin or apixaban, subsequent VTE prophylaxis (beyond day 12 or day of venography) may be determined by the site investigator as guided by local standard of care (see Permitted Medications, Section [8.8.2](#)). However, for subjects assigned to REGN9933, use of anti-coagulants for VTE prophylaxis is prohibited, because REGN9933 elevates aPTT through at least day 35 (see [Figure 1](#)).

Treatment is administered in an open-label manner because enoxaparin is packaged in pre-filled syringes, making blinding operationally challenging. In addition, performing the study in a blinded manner would require most (two thirds) of the participants to take placebo injections, which would have increased participant burden. To mitigate bias, participants will be randomized to treatment assignment. To further mitigate bias in outcome assessment, adjudication of outcomes related to VTE and bleeding (ie, results of venograms and any confirmatory study for symptomatic VTE; categorization of bleeding events) will be performed by a centralized adjudication committee (AC) that is blinded to treatment assignment (Section [6.3.3](#)).

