8.8.1. Prohibited Medications and Procedures

Administration of enoxaparin prior to TKA surgery is prohibited (Section 7.2.2 Exclusion criterion 10).

Anti-platelet therapy (except low doses of ASA ≤ 100 mg/day) is prohibited, unless indicated for treatment of an AE.

The following procedures/devices are prohibited after study drug has started:

- Use of spinal or epidural analgesia post-operatively
- Pneumatic compression devices

Subjects are prohibited from donating blood products through the EOS visit. Subjects are prohibited from donating sperm through the EOS visit. Subjects are prohibited from having planned, elective surgeries (except for TKA performed on day 1) through the EOS visit.

For patients assigned to the REGN9933 treatment arm, anticoagulant medications (including, but not limited to, vitamin K antagonists, heparins, DOACs) are prohibited after study drug has been started, unless they are indicated for treatment of an AE.

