8.8.2. Permitted Medications

Use of standard-of-care medications not listed as prohibited will be allowed.

For subjects assigned to either the enoxaparin or apixaban treatment arm, continued VTE prophylaxis (after completion of protocol-defined treatment, ie through the day of venography [or day 12, whichever is earlier]) is permitted, if deemed necessary by the site investigator based on local guidelines and/or clinical judgment. For the choice of agent to be used for subsequent VTE prophylaxis, it is preferred that the originally assigned treatment (ie enoxaparin or apixaban) is used. However, it is permissible to use other agents, as long as they are consistent with local regulations and standard of care for VTE prophylaxis after TKA surgery.

COVID-19 vaccination and any other vaccination can be administered as deemed necessary per the investigator based on his/her practice, standard of care, or as required based on mandatory vaccination programs. Vaccination is suggested to be administered preferably at least 1 week before the first dose of study drug (Section 7.2.2 Exclusion criterion 22), or at the earliest, 21 days following the last dose of study drug. Live-attenuated vaccines are generally not recommended during the study; however, use is allowed per the investigator's discretion.

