5.3. Prior / Concomitant Medications

The prior and concomitant medication will be descriptively summarized by treatment group on the SAF, sorted by decreasing frequency of ATC Level 2 and ATC level 4 of the total group. The use of anti platelets, anticoagulants (outside of assigned treatments), and NSAIDs may be included if deemed necessary.

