5.8.1. Analysis of Adverse Events

AE incidence tables will be presented for each treatment group, including the number (n) and percentage (%) of participants experiencing an AE, where multiple instances of the same event

occur in the same participant the event will be counted only once for that participant. The denominator for computation of percentages is the number of participants in each treatment group.

Treatment Emergent Adverse Events (TEAEs) are defined as AEs with either initial onset after the first dose of study treatment or that worsen after the first dose of study treatment. The number and proportion of participants reporting TEAEs will be summarized by SOC and PT.

Overall TEAE summary

The overall summary of TEAEs will be provided with number and proportions of participants with any:

- TEAEs
- Treatment-emergent serious adverse events (TE-SAEs)
- TEAEs of special interest (TE-AESI)
- Summary of deaths

TEAE incidence

Number and proportions of participants reporting TEAEs will be summarized for the following TEAEs:

- TEAEs
 - TEAEs by primary SOC and PT
 - TEAEs by primary SOC, PT and severity
 - TEAEs related to study drug by primary SOC and PT
 - Treatment-related TEAEs by primary SOC, PT and maximum severity
 - TE-AESI by primary SOC and PT
 - TEAEs leading to permanent treatment withdrawal by primary SOC and PT
- TE-SAEs
 - TE-SAEs by SOC and PT
 - Treatment-related TE-SAEs by primary SOC and PT
- TEAEs leading to death by primary SOC and PT

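### TEAE, bleeding and VTE results accumulated to end of study compare treatment strategies, because only the comparator arms may continue prophylaxis after venography or day 12, and the SAP does not plan the tables that would show this

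*Protocol*

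**What the plan says.** **Who may receive what after venography or day 12.** Protocol 8.8.2 opens the option to two arms: "For subjects assigned to either the enoxaparin or apixaban treatment arm, continued VTE prophylaxis" is permitted at the investigator's judgment. On the choice of agent, "it is preferred that the originally assigned treatment (ie enoxaparin or apixaban) is used", but "it is permissible to use other agents, as long as they are consistent with local regulations and standard of care". For the REGN9933 arm, Protocol 3.2.1 says that "for subjects assigned to REGN9933, use of anti-coagulants for VTE prophylaxis is prohibited", giving as its reason that "REGN9933 elevates aPTT through at least day 35". Protocol 8.8.1 adds that in this arm anticoagulants "are prohibited after study drug has been started, unless they are indicated for treatment of an AE".

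**What is counted to end of study.** Protocol 4.1.2 makes TEAEs through end of study a secondary endpoint and gives no other TEAE window. End-of-study VTE and bleeding are exploratory (Protocol 4.1.3). SAP 4.4.3 and 5.7.2 put end-of-study VTE into the Bayesian logistic model. SAP 4.5.2 summarises bleeding by arm, both to venography or day 12 and to end of study.

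**How TEAEs are defined.** SAP 5.8.1 says TEAEs "are defined as AEs with either initial onset after the first dose of study treatment", or that worsen after it. There is no end date and no split by period. Protocol 9.1 defines on-treatment and follow-up periods for safety variables and Protocol 11.4.5.1 refers to them, but neither document lists a summary by period.

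**What is tabulated on later anticoagulants.** SAP 5.3 requires a concomitant-medication table by arm and ATC class. The targeted summary is optional: "The use of anti platelets, anticoagulants (outside of assigned treatments), and NSAIDs may be included if deemed necessary".

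**The concern.** The follow-up period is not managed alike across the arms. Two arms may receive further prophylaxis and the third may not, and the documents do not say how the end-of-study results should be read in that light.

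What is at stake is mainly the secondary TEAE endpoint. A bleed on day 25 in an enoxaparin participant who continued prophylaxis counts in the enoxaparin column, next to REGN9933 participants who could not have continued. The reader cannot tell how many comparator participants continued, on what drug, or for how long. The optional anticoagulant summary would not fill the gap, because it leaves out assigned treatments, and those are the preferred agents for continuing. The exposure summary in SAP 5.6 is confined to the treatment period and is not stated to cover drug continued beyond protocol-defined dosing.

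**Working it through.** The plan gives no figure on this point to reproduce. The check has three parts.

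**1. How much of the window is involved.** Follow-up is 75 days (Protocol 3.2.1) and protocol-defined treatment ends by day 12. Days 13 to 75 number 75 − 12 = 63, and 63/75 = 84%. This is calendar time, not exposure. Protocol 3.2.1 notes that enoxaparin can be extended up to 35 days under its label. Taking day 35 as an approximate end, days 13 to 35 number 23, and 23/75 = 31%.

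**2. VTE (illustration).** Inputs from Protocol 11.2: 13% on REGN9933 and 22.4% on enoxaparin. Assumptions: late symptomatic VTE risk q = 0.5–2%; uptake u = 0–100%; relative risk of late VTE on extended prophylaxis RR = 0.4–0.6.

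- Day-12 OR = (0.13/0.87)/(0.224/0.776) = 0.518.
- End-of-study risk on REGN9933 = 0.13 + 0.87q.
- End-of-study risk on enoxaparin = 0.224 + 0.776q[1 − u(1 − RR)].
- Largest case, q = 0.02: REGN9933 = 0.1474. Enoxaparin with u = 0 is 0.2395, giving OR 0.549. With u = 1 and RR = 0.4 it is 0.2302, giving OR 0.578.
- The part due to prophylaxis is 0.578 − 0.549 = 0.029. At q = 0.005 and the same u and RR it is 0.533 − 0.526 = 0.007.

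**3. Bleeding or TEAEs with equal underlying risk in both arms (illustration).** All inputs are assumptions: risk b0 = 1–3% up to day 12, risk b1 = 1–3% after it, comparator uptake u = 25–100%, bleeding RR on extended prophylaxis = 1.5–3.

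- REGN9933 = b0 + (1 − b0)b1.
- Comparator = b0 + (1 − b0)b1[1 + u(RR − 1)].
- Example, b0 = 0.01, b1 = 0.03, u = 0.5, RR = 2: REGN9933 = 0.01 + 0.99 × 0.03 = 0.0397. Comparator = 0.01 + 0.99 × 0.03 × 1.5 = 0.0546. OR = 0.717 instead of 1.00.

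| Assumptions | End-of-study OR, REGN9933 vs comparator |
|---|---|
| b0 3%, b1 1%, u 25%, RR 1.5 | 0.97 |
| u 50%, RR 2, all b0 and b1 | 0.72–0.89 |
| b0 1%, b1 3%, u 100%, RR 3 | 0.38 |

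These figures give REGN9933 no activity of its own after day 12, which the protocol contradicts. In the worked example, if its residual activity also multiplied late bleeding by 1.5, both arms would stand at 0.0546 and the OR would be 1.00. A real late effect of REGN9933 would then be hidden rather than a false advantage created. The size and sign therefore depend on uptake and on residual activity. The documents give no figure for uptake and none for the effect of residual activity on bleeding.

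**The case against.** Several points on the other side are sound.

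- **An early window already exists for VTE and bleeding.** A reader might infer that the SAP never separates the periods. It does so for these outcomes: VTE through day 12 (SAP 4.4.1–4.4.3) and bleeding through venography or day 12 (SAP 4.5.2) are reported apart from the cumulative results. What is absent is a summary of the later period alone and, for TEAEs, any split.
- **Some tabulation is mandatory.** A reader might infer that anticoagulant use could go wholly unreported. The required ATC level 2 and 4 table by arm would show anticoagulants entered as concomitant medication. It is not stated to show timing or indication, and continued assigned drug may be missed if it is recorded as study drug.
- **The affected outputs rank low.** End-of-study VTE and bleeding are exploratory, and the adverse-event summaries are descriptive (SAP 11.1, Table 2). Only one secondary endpoint is involved.
- **The direction is not fixed.** A reader might infer a bias in favour of REGN9933 on safety. The documents do not support that, because REGN9933 raises aPTT to at least day 35. Comparator participants who do not continue have no relevant drug level within a few days of the last dose (Protocol 3.2.1).
- **Late events are not attributed blindly.** Related TEAEs are tabulated separately (SAP 5.8.1), and causality assessment considers concomitant medication (Protocol 10.2.6).
- **The effect may be within noise.** Suppose continuing prophylaxis added 2 points of clinically relevant bleeding (an assumption). Even at full uptake the shift is 2 points, against a 95% half-width of 1.96 × √(2 × 0.02 × 0.98/120) = 3.5 points at 2% rates.

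These points narrow the concern to reporting and interpretation. They do not supply the TEAE split or the missing table.

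**Conclusion.** The concern holds in a limited form. The asymmetry is explicit, so outcomes accumulated to end of study compare treatment strategies. This matters for the secondary TEAE endpoint and for the exploratory end-of-study bleeding and VTE outputs.

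The primary endpoint and the secondary bleeding endpoint are largely unaffected. One small leak remains: a comparator participant with venography on day 8 may begin extended prophylaxis inside the through-day-12 VTE window.

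The VTE distortion is likely small, at most about 0.03 on the odds ratio under the assumed ranges. For bleeding and TEAEs it could be anything from negligible to material (0.97 to 0.38 where the underlying risks are equal). That range rests entirely on assumed uptake, relative risk and event rates, and on ignoring REGN9933's residual activity. No claim about net direction is justified. The change is worth making because it affects what the secondary safety endpoint can support, and it is cheap.

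**What to change.** 1. **SAP 5.8.1:** summarise TEAEs separately from first dose to the end of protocol-defined treatment (venography or day 12, whichever is earlier) and from then to end of study. Protocol 9.1 ends its on-treatment period at day 12 regardless of venography, so the SAP should state its own cut-point. Add a later-period summary for bleeding (SAP 4.5.2) and VTE (SAP 5.7.2) beside the existing windows.
2. **SAP 5.3:** make mandatory a by-arm table of anticoagulant use after venography or day 12, including continued assigned drug, with agent, start, duration and, where recorded, whether for prophylaxis or treatment.
3. **Labelling:** describe end-of-study contrasts as treatment-strategy comparisons. The split makes the imbalance visible but does not remove it, so the later-period results need the same label.

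The cost is a few extra tables, with small event counts in the later period. Medications are recorded to the end-of-study visit (SAP 4.3). The documents do not say whether indication is captured as prophylaxis or treatment, or whether continued assigned drug is entered as concomitant medication, so both should be checked before the table is specified. No change to clinical management is involved.

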3.2.2. Rationale for Dose Selection

A single 300 mg IV dose of REGN9933 has been chosen based on data from a single ascending dose study with REGN9933 in healthy volunteers (study R9933-HV-2107) which explored the safety, PK, and PD effects, of single IV doses of REGN9933 up to 300 mg. Study participants each received a single 0.5 hour IV infusion of REGN9933 or matching placebo and blood samples for measurement of concentrations of REGN9933 in serum and PD assays (including Factor XI activity, PT and aPTT) were collected at intervals. REGN9933 pharmacokinetics were non-linear across the 3 to 300 mg dose range in a manner consistent with target-mediated drug disposition. REGN9933 treatment had no apparent effect on PT, but produced a rapid, dose-dependent decrease in Factor XI activity and a rapid, dose-dependent increase in aPTT without significant safety, tolerability, or bleeding findings. Preliminary analyses of available data are summarized in Section 5.2 of the IB.

Single doses of REGN9933 \geq 100 mg produced sustained inhibition of FXI activity and increases in aPTT in all treated individuals (Figure 1). Based on these observed data it is expected that a REGN9933 dose of 300 mg will maintain maximal inhibition of FXI activity and maximal effects on aPTT (~2.8-fold change from baseline, corresponding to absolute aPTT values of approximately 60 to 80 sec) in all individuals for \geq 14 days. Pharmacodynamic data from study R9933-HV-2107 showed that aPTT values had returned to within 10% of normal values 64 days following the 300 mg dose.

REGN9933 exposures from a 300 mg IV dose are substantially lower than corresponding exposures at the non-clinical toxicology no observed adverse effect level (NOAEL). Observed average total REGN9933 exposures from a 300 mg dose in study R9933-HV-2107 were $>60\times$ lower than average exposures at the NOAEL dose (100 mg/kg IV) in the 5-week REGN9933 GLP monkey toxicology study (R9933-TX-20070).

Figure 1: Mean (+SD) Change from Baseline in a) Factor XI Activity and b) aPTT by Nominal Time and by Dose in Healthy Volunteers (0-63 Days, Linear Scale, Study R9933-HV-2107)

Arithmetic means, error bars represent standard deviation.

Previous studies investigating the use of FXI inhibitors for prevention of post-operative VTE have shown that efficacy correlates with the magnitude of treatment effects on aPTT; maximum efficacy was achieved at doses which maintained near-maximal increases in aPTT (ie 2 to 3x increase from baseline) throughout the assessment period eg ([Verhamme, 2021](#)). It is therefore anticipated that a 300 mg dose of REGN9933 will produce maximal efficacy for prevention of VTE in this clinical setting.

3.3. Risk-Benefit

Recognizing that the “Coronavirus Disease 2019” (COVID-19) pandemic will have an impact on the conduct of clinical trials, the Sponsor does not intend to screen any participants in this study until the impact of the COVID-19 pandemic is deemed manageable and no longer interfering with the conduct of trials at individual sites, and participants can safely participate in this study. Until then, the Sponsor plans to obtain approvals from Health Authorities/Ethics Committees to enable initiation of study sites for this study, as allowed by local laws and regulations.

For information regarding the permitted timing of COVID-19 vaccinations, see Section [7.2.2](#) Exclusion Criteria, criterion #[22](#), and Section [8.8.1](#) Prohibited Concomitant Medications and Procedures.

A risk-benefit statement with respect to the overall development program is provided in Section [7](#) of the IB.

3.3.1. Risk-Benefit for REGN9933

REGN9933 is a monoclonal antibody that binds to FXI and inhibits activation by the intrinsic pathway of the coagulation cascade.

There is no clinical evidence that REGN9933 prevents VTE in post-surgical patients, including TKA. However, several lines of evidence suggest that inhibition of the intrinsic pathway, and FXI specifically, may reduce the incidence of VTE. As discussed in Section 1, FXI deficiency is associated with reduced risk of VTE in humans. Furthermore, clinical studies with other FXI blockers have shown reduced incidence of VTE after TKA relative to enoxaparin ([Büller, 2015](#)) ([Verhamme, 2021](#)) ([Weitz, 2020](#)) ([Weitz, 2021](#)). Extrapolation of these data to REGN9933 may be limited since it has a distinct mode of binding to FXI. Single doses of REGN9933 have been studied in healthy volunteers (study R9933-HV-2107) and REGN9933 treatment produced a rapid, dose-dependent decrease in FXI activity and a corresponding rapid, dose-dependent increase in aPTT, indicating inhibition of the intrinsic pathway (refer the [Section 5.2](#) of the IB for preliminary analyses of available data). The magnitude of FXI inhibition and PTT elevation are comparable to those seen with other FXI blockers at doses that reduced VTE after TKA. Furthermore, the key design elements of this study are similar to those in the previous FXI inhibitor trials referenced above.

Post-TKA VTE are generally asymptomatic. In the aforementioned studies comparing FXI targeted therapy versus enoxaparin in post-TKA VTE, <2% of participants experienced a symptomatic VTE. In addition, of all of the participant who experienced a VTE, <15% were symptomatic. Even with placebo, only 13% of patients experienced a proximal DVT after TKA ([Lovenox \[Package Insert\], 2022](#)).

Mitigation and monitoring for VTE risk include:

- Participant selection will exclude those with history of thromboembolic disease or thrombophilia
- Routine, protocol-specified monitoring for clinical signs of VTE
- Scheduled venogram can identify subclinical DVTs that may be treated with therapeutic anticoagulation

Bleeding is an important potential risk of treatment with any anticoagulant, including REGN9933. As discussed in Section 1, genetic FXI deficiency is not associated with spontaneous bleeding. Clinical studies with other FXI inhibitors have not shown increased risk of bleeding, even when dosed prior to TKA surgery.

To date, no study drug-related AEs or SAEs have been observed with REGN9933 in the healthy volunteer study R9933-HV-2107 (as discussed in Section 1).

In preclinical toxicology studies with cynomolgus monkeys, REGN9933 was administered at doses up to 100 mg/kg via SC injection and 100 mg/kg via IV infusion (once weekly for 5 weeks). There were no significant increases in PT, and bleeding events were similar between treated and non-treated animals.

Mitigation and monitoring for bleeding risk include the following:

- Participant selection will exclude participants with identified bleeding disorders or risk factors for significant bleeding.
- During the trial, participants will be monitored for bleeding events.
- Coagulation parameters will be followed for all participants.
- Moderate to severe bleeding (both spontaneous and non-spontaneous) will be considered adverse events of special interest (AESI) with expedited reporting.
- In the event participants need to seek medical attention during the follow-up period, they are provided a card that details that they are enrolled in a study of a novel anticoagulant targeting FXI upon clinic discharge following surgery.

As described in the Study Stopping Rules (Section 6.1.1.1), the Independent Data Monitoring Committee (IDMC) will monitor the overall rates of both VTE and bleeding, and can recommend pausing of REGN9933 dosing if there are concerns of increased VTE or bleeding risk relative to enoxaparin.

Other important potential safety risks include systemic hypersensitivity reactions, embryofetal toxicity, and immunogenicity. With regard to potential embryofetal toxicity, WOCBP and men whose sexual partners are not willing to practice highly effective contraception are excluded from this study. For more information on mitigation and monitoring for these potential risks, please refer to [Section 6](#) of the IB.

3.3.2. Risk-Benefit for Active Comparator and Calibrator

As with other anticoagulants, participants taking apixaban or enoxaparin are to be carefully observed for signs of bleeding. In countries where enoxaparin and apixaban have been granted marketing authorization, the regulatory bodies have considered that the benefit of therapy has outweighed the risk for the indications granted, including VTE prophylaxis after TKA. All investigators must comply with and satisfy all requirements for the local risk management plan or equivalent for apixaban and enoxaparin where applicable and before dosing participants. In this study, participants will be closely monitored for bleeding, with oversight of the study by the IDMC (Section 6.3.1). Emergent evaluation and management of bleeding should be conducted according to standard local protocols aligned with bleeding management guidelines, as described in Section 8.2.

